7.4 Procedures for Study Closure

7.4.1 Routine study close-out

The study will end when Pelex has obtained all data necessary to complete its studies of the test product. Study close-out will follow Pelex standard procedures and may include, but is not limited to, review of regulatory documents, collection of completed case report forms, reconciliation of study records, removal or destruction of ancillary study supplies, and informing the Investigator of remaining obligations (e.g., record retention, final report submission to the IRB, financial disclosure updates, etc.).

7.4.2 Suspension or premature termination of the study

This study may prematurely terminate at any time because of a regulatory authority decision, a change in opinion of the IRB, or at the discretion of the Investigator or Sponsor. If this trial is temporarily suspended or prematurely discontinued, Pelex will promptly notify the Investigator(s) and provide instructions. If the study is temporarily suspended, Pelex will provide guidance on timing and procedures for resuming the study. If the study is prematurely discontinued, all study materials must be collected and all study forms completed to the extent possible. All such materials must be returned to Pelex upon request. Reasons for termination of the study or a study site may include, but are not limited to, the following:

- The risks and benefits of continuing the study have been reassessed, and the risks outweigh any potential benefits.
- The incidence of AEs constitutes a potential health hazard to the subjects.
- New scientific data do not justify a continuation of the study.
- The investigator or study site exhibit serious and/or persistent non-adherence to the clinical study protocol and/or applicable regulatory requirements.
- The Sponsor decides to terminate the study at any time for any other reason.

8 DATA QUALITY ASSURANCE

The study screening questionnaire, pre-study survey, post-use survey, and post-study survey are all forms requiring input from subjects. Pelex will endeavor to use electronic forms of data capture whenever possible. Possible forms of electronic data capture include Google

forms and SurveyMonkey. These forms will be configured such that only [name] has access to the raw information in order to protect patient health information.

While obtaining the informed consent, [name] will ask the subject whether she is able to use electronic data forms. In the event that the subject indicates that she is unable to use electronic data forms, then the study team will include a paper journal in the study package. The study package will be returned to [name] who will be responsible for converting the paper form to an electronic format, anonymizing the electronic version, and archiving or destroying the paper form.

Beyond subject input, the study device are intended to collect physiological parameters and store this data on the device. The data will be salvaged when the study materials are returned to the study team. The device data will only be stored using the anonymous subject identifier. Data stored on the device hardware that is returned to the study team will be recovered by [name] following a protocol that has been established with the primary device manufacturer, Arduino. Anonymized recovered data will be collectively stored in a password protected data server or database. The raw data will be backed up at least once to local storage.

The data will be processed through reproducible measures, such as by writing start-to-finish code. When data processing is complete, this code will be applied to a copy of backed-up raw data to confirm the reproducibility of the analysis and integrity of the raw data.

9 STATISTICAL METHODS

9.1 Determination of Sample Size

This study is exploratory and not designed to establish non-inferiority or superiority. Therefore, determining a sample size for the purposes of statistical significance is not necessary.

9.2 Bias Minimization

All subjects meeting the specified eligibility criteria will be enrolled on a first-come, first-serve basis.

9.3 Planned Analyses

Specific study parameters to be analyzed will be the maximum pelvic floor contraction at study entry and exit, as well as maximum sustained contraction at study entry and exit. Objective clinical response to use of device in improving SUI symptoms will also be captured per the symptom questionnaires, which will be entered into an electronic record, and then all responses will be aggregated.

10 ADVERSE EVENT REPORTING

10.1 Non-Device-Associated Adverse Events

Adverse events occurring during the enrollment period should be documented by the Investigator in progress notes, but will not be collected or analyzed by Pelex unless considered serious by the Investigator.

Serious adverse events (SAEs) encountered during study enrollment will be documented by the Investigator and reported to Pelex immediately upon discovery. SAEs are defined under current Good Clinical Practice (cGCP) guidelines as events that result in one or more of the following:

- life-threatening illness or injury;
- permanent impairment of a body structure or a body function;
- medically necessary in-patient hospitalization;
- medical or surgical intervention necessary to prevent permanent impairment to body structure or function; or
- fetal distress, fetal death, or congenital abnormality.

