Methodology Overview	
This will be a prospective cohort study of women > 18 years of age with symptoms of stress urinary incontinence, recruited via an online recruitment tool.
 
After screening, patients meeting inclusion criteria will be given a study brochure, and then given instructions on how to indicate desire to participate in the study. The patient will then be contacted for study participation, including explanation of study and details and completion of Informed Consent. Participants will then complete a pre-treatment urinary incontinence symptom questionnaire(ICIQ).
 
After completion of the above, the participants will then be given a Pelex Upp study, in addition to educational materials on use of the device, and a treatment schedule. Participants will perform a standardized biofeedback-mediated pelvic floor muscle training program with the study device 10 minutes a day, five times a week for 4 weeks. There will be a mid-study check in to assure all devices are functioning appropriately. At the end of the study, participants will complete a post-treatment urinary incontinence symptom questionnaire(ICIQ).
 
Endpoint of the study will be change in stress urinary incontinence symptoms as measured by the ICIQ. The ICIQ will be collected at 2 time points: before study entry, and at study close.

ABBREVIATIONS

PFMT	Pelvic floor muscle training
SUI	Stress urinary incontinence
OAB	Overactive bladder
UI	Urinary incontinence
PFM	Pelvic floor muscles
US/USA	United States of America

TABLE OF CONTENTS

1	INTRODUCTION	11
2	DESCRIPTION OF THE INVESTIGATIONAL PRODUCT	11
2.1	Overview	11
2.2	Proposed Intended Use Statement	11
3	STUDY OBJECTIVES	11
4	STUDY OVERVIEW	12
4.1	Study Approach	12
4.3	Study Duration.....	13
5	STUDY POPULATION	14
5.1	Sample Size and Target Study Population	14
5.1.1	Sample size	14
5.1.2	Study population	14
5.1.3	Alignment with intended study population.....	14
5.1.4	Alignment with intended use of the device.....	14
5.2	Recruitment Methods	14
5.2.1	Recruitment for Study	14
5.2.2	Duration of study activities.....	14
5.3	Patient Selection	15
6	STUDY MATERIALS	15
6.1	Investigational Product.....	15
6.1.1	Identity of the investigational product and accessories	15
6.1.2	Safety issues.....	16
6.1.3	Handling, storage, accountability.....	16
6.1.4	Required training.....	16
6.1.5	External studies.....	17
6.2	Other Study Materials	17
6.2.1	Materials to be provided by study site.....	17

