However, despite the advantages these devices provide, there are still significant barriers to use. Due to the way biofeedback in conjunction with PFMT must be performed, specifically capture of the contraction and relaxation of the PFM, devices designed for use in these setting are either invasive (inserted into the vagina or rectum) or require placement by a trained professional (surface EMG electrodes). This presents a barrier to use for patients, and an opportunity for innovation. Specifically, the product under investigation, the Pelex Upp is designed for use at home for biofeedback plus PFMT sessions. It has a non-invasive patient interface that takes advantage of the unique anatomical properties of the perineum, the skin between the anus and vagina or scrotum, allowing the patient to perform PFMT plus biofeedback without the need for invasive devices or professionally placed electrodes.

The aim of the present pilot study is to determine efficacy of our product in the treatment of SUI in a home setting. Since PFMT plus biofeedback is considered standard of care in patients with SUI who are therapy-naïve, the study subjects will be exposed to no greater than normal risk associated with treatment. Study subjects will undergo evaluation by a treating physician and will have prescribed a treatment regimen typical for the disease process.

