10.2.2 Reporting of device-associated adverse events

Any adverse event that results in serious injury or death and any type of unanticipated adverse device effect, regardless of seriousness or severity, must be reported to the Investigator once when site becomes aware of the event. Initial reports may be partial and should be updated as additional information becomes available. All unanticipated adverse device effects and all serious adverse events should be reported to the Investigator's IRB in accordance with the IRB reporting requirements.

SAEs will be reported using an Unanticipated Adverse Device Effects (UADE) form, which serves the dual role of capturing pertinent SAE information per industry guidelines and capturing device information pertinent to medical device standards. Other serious events that affect the rights, safety, or welfare of subjects must also be documented on the UADE form and must be reported immediately to Pelex and to the Investigator's IRB according to that IRB's policies.

All SAEs that occur during the study period, whether considered to be related to the investigational product or not, will be reported within 24 hours of knowledge of the event to the sponsor contact below via an EDC notification.

Although all information required for completion of an SAE report form may not be available within the specified time period, the following minimal initial information should be reported: Subject ID #, Site #, an identifiable reporting source name and contact information (e.g. investigator/study coordinator), which of the 6 SAE criteria identified above resulted in the event being deemed “serious”. IRB reporting requirements may also apply for SAEs.

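### Section 10 says where adverse events are written down and how serious ones are forwarded, but describes no active way of finding them in a home-use study

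*Protocol*

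**What the plan says.** **Recording and forwarding.** Section 10.1 says that adverse events "should be documented by the Investigator in progress notes", and that the sponsor neither collects nor analyses them unless the Investigator judges them serious. SAEs are documented by the Investigator and "reported to Pelex immediately upon discovery". Section 10.2.2 adds a separate route: "SAEs will be reported using an Unanticipated Adverse Device Effects (UADE) form", and all SAEs, related or not, "will be reported within 24 hours of knowledge of the event", by an EDC notification. IRB reporting also applies.

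**Setting and contacts.** Section 4.1 gives the aim as to "determine efficacy of our product in the treatment of SUI in a home setting". The Synopsis sets sessions five times a week for four weeks. It describes the mid-study contact as follows: "There will be a mid-study check in to assure all devices are functioning appropriately". The ICIQ is taken before entry and at close. The study materials table in Section 7.1 also lists an initiation check-in, a post-use questionnaire and a post-study questionnaire, without content. The same section leaves follow-up with care providers to the patient. Section 4.1 mentions evaluation by a treating physician but gives no visit or time for it.

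**Expected harms.** Section 6.1.2 names skin abrasion and contact allergic reaction from the adhesive sensor array on bare skin.

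**The concern.** Every step in Section 10 assumes that the site already knows of the event. A note can be written only after somebody has learned of it, and the SAE rules start at discovery or knowledge. In a clinic-based trial, scheduled visits would supply that knowledge. Here the women are recruited online and treat themselves at home, and no visit is scheduled during treatment at which progress notes would naturally arise.

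If nobody asks, an empty record cannot be told apart from an unasked question. That matters for two statements in the protocol. Section 7.4.2 lists the incidence of adverse events among the possible reasons for termination, and Section 11.1 asserts no greater risk than standard pelvic floor training with biofeedback. Unsolicited reports are a poor basis for judging either. Minor skin reactions are the expected device harm, and a woman may well not think them worth reporting.

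**Working it through.** The protocol gives no figure on this point, so there is none to reproduce. The check is a listing of contacts and forms, followed by an illustration of size.

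**Contacts and forms described**

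| Contact or form | Where | Stated content | Adverse events mentioned? |
|---|---|---|---|
| Consent, screening, pre-study questionnaire | Synopsis; 7.1; 8 | Eligibility, consent, baseline ICIQ | No; precedes treatment |
| Initiation check-in | 7.1 table | None | Not stated |
| Mid-study check-in | Synopsis; 7.1 table | Device function | No |
| Post-use questionnaire | 7.1 table; 8 | None | Not stated |
| Post-study questionnaire | Synopsis; 7.1 table; 8 | ICIQ at close | Not stated |
| Physician evaluation | 4.1 | No visit or time | Not stated |
| Care-provider follow-up | 7.1 | At the patient's choice | No |

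Planned exposure: 5 sessions a week × 4 weeks = 20 sessions per woman; 20 × 5 women = 100 sessions. Against these, no contact or form is described as asking about adverse events. The exit ICIQ could show worsened incontinence, but only at the end, and it is not described as covering skin reactions.

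**Fit with the expected harms.** Section 10.1 is headed as non-device-associated. Section 10.2 covers serious events and unanticipated device effects. A non-serious, anticipated skin reaction therefore fits neither heading. If it is handled under 10.1, the sponsor does not collect it.

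**Illustration.** Input from the protocol: n = 5. Assumptions, none of them in the protocol: true event rate per woman p = 0.20; fraction of events that reach the site r = 1, 0.5 or 0.25.

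P(no event seen) = (1 − p·r)^5

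- r = 1: (1 − 0.20)^5 = 0.328, or 33%
- r = 0.5: (1 − 0.10)^5 = 0.590, or 59%
- r = 0.25: (1 − 0.05)^5 = 0.774, or 77%

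Upper limit after 0 events in 5, one-sided 95%:

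- all women asked, all events reported: 1 − 0.05^(1/5) = 0.451, or 45%
- half of events reported: 0.451 / 0.5 = 0.90, or 90%

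**The case against.** A reader might go further in four ways. The documents do not support these readings.

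- **That SAEs are kept only in progress notes.** They are not. Section 10.2.2 gives them their own form, an EDC notification within 24 hours and IRB reporting.
- **That events are known only if volunteered.** This cannot be shown. The content of the initiation check-in, the post-use questionnaire and the post-study questionnaire is not given, the workflow figure is not available, and Section 1 says that other patient feedback will be captured. Any of these could include a health question.
- **That there is no clinical contact at all.** Section 4.1 mentions a physician evaluation, Section 7.2.1 lists medical records among source documents, and the withdrawal criterion of worsening symptoms in Section 5.3 presupposes some symptom reporting. None of these gives a timed contact during treatment.
- **That an empty record will be reported as absence of harm.** No passage says so. Section 3 has no safety objective and Section 9.3 no safety analysis.

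Nor is it a defect that the 24-hour limit runs from knowledge, since nobody can report an unknown event.

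The illustration rests on assumed rates and applies one reporting fraction to all events, although SAEs and minor skin reactions need not be reported equally. With perfect asking, five women would still leave an upper limit of 45%, so the sample size is already a severe limit. All of this stands and narrows the point. What remains is that the protocol describes no active ascertainment, and that doing so at contacts already planned would cost very little.

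**Conclusion.** The point holds as a gap in detection. Recording and forwarding are described; finding out is not. Unless an undescribed questionnaire or check-in asks, both non-serious events and SAEs come to light by spontaneous report during 20 home sessions per woman.

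The size depends on how much goes unreported, which the protocol does not allow one to estimate. Under the assumed 20% rate, moving from full to quarter reporting raises the chance of a blank record from 33% to 77%. The conclusion rests on the available text alone and would fall away if a listed questionnaire already contains such a question. For a five-woman, four-week, non-invasive pilot this is a cheap improvement, not a flaw that invalidates the study.

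**What to change.** In Section 10, so that it covers both 10.1 and 10.2, state that one fixed open question is put to every woman: whether she has had any health problem or skin reaction since the last contact. Ask it at the initiation check-in, the mid-study check-in and the post-study questionnaire.

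Three consequential edits are needed:

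1. Add an eCRF field for yes or no with the date, completed for every woman at each contact, so that an answer of none is distinguishable from not asked.
2. Widen the purpose of the mid-study check-in in the Synopsis beyond device function.
3. Amend the sentence in 10.1 under which the sponsor does not collect or analyse non-serious events. Otherwise the answers would be gathered and then excluded, and the section would contradict itself.

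If a listed questionnaire already asks, say so in Section 10, and add the question only at the contacts that lack it.

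The cost is one question at three existing contacts and one eCRF field, with no new visit. The downside is a few more minor events to record.

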1 INTRODUCTION

Pelex, Inc. is a medical device company that is dedicated to addressing pelvic health disorders. The company is developing a non-invasive medical device that uses electromyography and neurostimulation to treat incontinence and other pelvic floor disorders. In support of its research and development efforts, Pelex is conducting a clinical study to assess the efficacy and usability of the electromyography component of the company's pelvic health product. Five patients suffering from stress urinary incontinence, a form of pelvic floor disorder, will be recruited to participate and the duration of participation is expected to be four weeks. The result of this study will be used to verify that the underlying technology functions as expected, identify subject preferences for device form factor and other design decisions, and capture other patient feedback.

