6.1.2 Safety issues

The device under investigation is completely non-invasive, and qualifies as a non-significant risk device based on Title 21 CFR 812.2 (c). Safety issues would include skin abrasions and contact allergic reactions from contact of bare skin with the flexible circuit array, which has a mild adhesive applied to it

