12.3 Access to Source Documents

Pelex or its agents and appropriate regulatory authorities shall be granted direct access to all study-related documents to perform verification that the protocol and all applicable current Good Laboratory Practices (cGLPs), Good Clinical Practices (GCPs), and regulations are being followed and to confirm that study documents are complete and accurate. It is important that Investigator(s) and their relevant personnel be made available during monitoring visits and any audits or inspections, and that sufficient time is allotted for the process.

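### Non-serious, anticipated device effects, including the skin reactions that Section 6.1.2 names, fall outside the sponsor's routine collection and tabulation

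*Protocol*

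**What the plan says.** Section 6.1.2 identifies the expected harms: "Safety issues would include skin abrasions and contact allergic reactions from contact of bare skin with the flexible circuit array". The array carries a mild adhesive.

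Section 10.1 is headed as covering adverse events not associated with the device, but its first sentence speaks of adverse events without that limit. They are to be "documented by the Investigator in progress notes, but will not be collected or analyzed by Pelex unless considered serious by the Investigator". The same section holds the protocol's only list of criteria for a serious adverse event (SAE).

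Section 10.2 deals with device-associated events. Section 10.2.1 defines an unanticipated adverse device effect (UADE) by two features: it is serious, and the plan has not already identified it in nature, severity or degree of incidence. Section 10.2.2 then requires reports to the Investigator for "Any adverse event that results in serious injury or death and any type of unanticipated adverse device effect, regardless of seriousness or severity". Reports to the sponsor within 24 hours cover SAEs, "whether considered to be related to the investigational product or not". Other serious events affecting subjects' rights, safety or welfare also go to the sponsor.

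Section 9.3 lists contraction measures and symptom questionnaires as the planned analyses. Section 7.4.2 lists the incidence of adverse events among the possible reasons for ending the study.

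**The concern.** The reactions most to be expected from this device are mild skin complaints, and these are the events for which the protocol provides no route to the sponsor's data. Participants use an adhesive array on bare skin at home. Section 1 says the results will help to "identify subject preferences for device form factor and other design decisions, and capture other patient feedback". How well the contact surface was tolerated bears directly on that purpose, yet it would have to be pieced together from progress notes or free feedback. Section 7.4.2 also makes event incidence a possible ground for termination, while Section 10.1 keeps non-serious events out of the data from which the sponsor would judge it.

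A statistical analysis plan cannot repair this. It can specify tables for events that are collected, but what is collected is set in the protocol, and 10.1 makes a positive statement of non-collection.

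**Working it through.** The plan gives no figure to reproduce. The main check sets the passages side by side.

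**Coverage by type of event**

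| Event | Provision | Reaches the sponsor's data? |
|---|---|---|
| Serious, related or not | 10.1 and 10.2.2 | Yes |
| Device-associated, non-serious, unanticipated | 10.2.2 asks for a report to the Investigator; the definition in 10.2.1 requires seriousness | Unclear |
| Not device-associated, non-serious | 10.1 | No, expressly |
| Device-associated, non-serious, anticipated (the 6.1.2 skin events) | None in 10.2; the text of 10.1 excludes them if it applies | No |

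The last row has the same answer on both readings of 10.1:

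- *By its text.* The exclusion covers adverse events generally. The two sections are not self-contained either: 10.2.2 asks "which of the 6 SAE criteria identified above resulted in the event being deemed" serious, and those criteria stand only in 10.1.
- *By its heading.* Section 10.1 does not apply to skin reactions, and no sentence in 10.2 takes them up.

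Other stated routes do not close the gap. The Synopsis gives the mid-study check-in the purpose of confirming device function. Section 9.3 plans no safety summary. Sections 7.2.1 and 8 describe the eCRF and surveys without naming an adverse event item.

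**Exposure** (Synopsis: "10 minutes a day, five times a week for 4 weeks"; 5 participants, Section 5.1.1)

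- Sessions per participant: 5 × 4 = 20
- Minutes per participant: 20 × 10 = 200
- All participants: 5 × 20 = 100 sessions, or 5 × 200 = 1,000 minutes

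**Chance that at least one of five participants is affected**

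The documents give no reaction rate, so the per-person rates p below are assumptions. The formula is 1 − (1 − p)^5, which treats participants as independent.

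| Assumed p | 1 − (1 − p)^5 |
|---|---|
| 5% | 1 − 0.95^5 = 0.226 |
| 10% | 1 − 0.90^5 = 0.410 |
| 20% | 1 − 0.80^5 = 0.672 |
| 30% | 1 − 0.70^5 = 0.832 |

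Solving for the rate that gives a chance t, p = 1 − (1 − t)^(1/5):

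- t = 0.50: p = 0.129, about 13%
- t = 0.80: p = 0.275, about 28%

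**What a count from five participants can show** (Clopper-Pearson, two-sided 95%)

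- 0/5: 0 to 0.522
- 1/5: 0.005 to 0.716

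The count would describe what happened in this study. It would not estimate a rate.

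**The case against.** The strongest objection is that the exclusion stands under a heading for events not associated with the device. On that reading 10.2 is merely silent about mild skin reactions, and silence is not a refusal to collect. This is fair as to wording, and it is why the gap appears only when 10.1 and 10.2 are read together. It changes the route to the gap and not the result.

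Second, coverage by 10.2.2 is arguably ambiguous. Section 6.1.2 gives the nature of the skin events but no severity or incidence, so some could count as unanticipated, and 10.2.2 then applies whatever their seriousness. Against this, 10.2.1 requires seriousness, and the report in question goes to the Investigator and the IRB. The ambiguity is real, but it gives the sponsor no count.

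Third, the post-use and post-study questionnaires, the check-ins and the eCRF are not shown and may ask about skin complaints. That stands as a limit on the claim.

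Fourth, the sponsor is not blind to these events. Under 12.3, "Pelex or its agents and appropriate regulatory authorities shall be granted direct access to all study-related documents"; Section 7.2.1 gives the sponsor access to the study database, and Section 12.1 returns study materials to it. With about five participants, a listing from progress notes would be little work. This also stands: what is lost is systematic collection and tabulation, not all knowledge.

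Last, the study is exploratory, its objectives are efficacy and ease of use, and the device is described as non-significant risk. That keeps the point moderate in weight. It does not remove it, because the remedy is nearly free.

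**Conclusion.** The point holds. As written, the protocol gives the sponsor no routine count of non-serious skin abrasion or contact reaction, the device's own named risks, over a planned 100 skin-contact sessions. Whether any such event would occur in five participants cannot be known from the documents: over assumed per-person rates of 5% to 30%, the chance of at least one affected participant runs from 23% to 83%. The loss is a descriptive count, and no efficacy result changes.

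The conclusion assumes that the unseen forms contain no skin question. If they do, the practical loss is smaller, but 10.1 and 10.2 still need to be made consistent with that collection. The change should be made; it is not critical to the validity of the study.

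**What to change.** 1. In 10.2, add a sentence: every adverse event the Investigator considers related to the device, serious or not, including skin abrasion and contact reaction, is recorded on the eCRF and summarised as the number of participants affected out of those treated.
2. Record the Investigator's relatedness judgement (yes/no) with each event. Section 10.2.2 already refers to relatedness for SAEs.
3. In 10.1, limit the exclusion to events judged not related to the device, as the heading implies.
4. Unless already there, add one skin-reaction question to the mid-study check-in and one to the post-study questionnaire.

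Two neighbouring inconsistencies can be settled in the same edit, although the point does not depend on them. Section 10.2.2 disregards seriousness for UADEs while 10.2.1 requires it, and 10.2.2 refers to six SAE criteria where 10.1 lists five. The passages must be reconciled.

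The cost is one sentence, one limiting phrase, one eCRF entry with a relatedness box (if not already present) and at most two questions in contacts already planned. The downside is a few more records and one relatedness judgement per event, for five participants.
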